8.2. Inclusion criteria

- Patients that are scheduled for vitrectomy surgery, cataract surgery or combined surgery, regardless of the indication
- Primary or repeat vitrectomy
- General or local anesthesia, or combination
- Patients Aged \geq 18 years

8.3. Exclusion criteria

- Patients aged $<$ 18 years old

9. PARTICIPANT SELECTION AND ENROLMENT

9.1. Identifying participants

The trial will be initiated only after the device manufacturer (DORC B.V.) has received a CE-label for both the surgical device (EVA Nexus) and its surgical supplies. Hence, no FAGG application will be necessary for this study.

Since no experimental device is used in this field observation study, the patient is not asked for permission to have the surgery done using this device, but approval is needed from the patient to use his/hers EMR data for a clinical trial. Patients that are not asked for study participation could also undergo surgery with the EVA Nexus device, since it will be fully approved for clinical use at the time of the study.

Hence, it is important to emphasize that whether the patient is included in trial has in no way any influence on the clinical care: the surgery might be performed with the same device, and the same clinical data will be recorded before, during and after the surgery. There are no supplementary study visits, nor is any specific study-related clinical or technical examination performed.

Patients will be asked for permission for inclusion in the study on the evening of the day of the surgery. After finishing all surgeries, the surgeon always does a round in the one-night-stay department to see the patients that were operated that day. During that post-operative patient briefing, the surgeon will ask the patient for inclusion in the trial and to sign the informed consent.

This 'approval after surgery' instead of asking before the surgery had several advantages:

- Although the patients follow exactly the same clinical path as in the standard-of-care (including the device used for the surgery), it is very disturbing for a patient to hear pre-operatively that he/she will be included in a clinical study. Patients usually do not understand that only the use of their EMR for a study also requires their informed consent and signature. Rather, patients that are asked for such approval before the surgery will experience more stress because they may (incorrectly) believe some experimental therapy is being done.
- The surgeon will not know in advance whether a patient will be included in the study. Indeed, when asked after the surgery, a patient may or may not give their consent for participation.

Hence, neither the decision to perform the surgery nor the scheduling of the surgery will be influenced by participation in the trial, further eliminating any possibility that participation in the trial may influence the clinical care of the patient.

However, in theory, a surgeon may decide not to ask permission for study participation in patients that have more surgical risk. For example: high myopia, very small eye size, previous ocular trauma etc. all make the surgery more prone for adverse events. Therefore, in this study, the investigator will ask ALL patients that were operated that day for their approval to participate in the trial and keep an (pseudonymized) list of how many patients refused participation. This way, this theoretical bias in patient selection is also omitted.

In case a patient prefers not to have their EMR used for this field observation study, the further clinical tract remains unaltered.

9.2. Consenting participants

Patients that are underwent phaco and/or vitrectomy surgery will be given the informed consent and will be asked to participate in the clinical trial.

Following Ethic Committee (EC) approval and before any investigation related procedure, potential participant must personally sign and date the latest approved version of the informed consent form before the EMR is used for this study.

Written and verbal versions of the participant information and Informed consent will be presented to the participants detailing no less than: the exact nature of the clinical investigation; the implications and constraints of the clinical investigation plan; the known side effects and any risks involved in taking part (if present). It will be clearly stated that the participant is free to withdraw from the clinical investigation at any time for any reason without prejudice to future care, and with no obligation to give the reason for withdrawal.

The participant will be allowed as much time as wished to consider the information, and the opportunity to question the Investigator, their GP or other independent parties to decide whether they will participate in the clinical investigation. Written Informed Consent will then be obtained by means of participant dated signature and dated signature of the person who presented and obtained the informed consent. The person who obtained the consent must be suitably qualified and experienced, and have been authorized to do so by the Coordinating/Principal Investigator. A copy of the signed Informed Consent will be given to the participants. The original signed form will be retained at the clinical investigation site.

In case of updates of the participant information and Informed consent the participant must personally sign and date the latest approved version of the informed consent form before any further clinical investigation specific procedures are performed.

For this clinical trial, signature for approval from the patient will be obtained at the evening of the day of the surgery (see above).

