7.2 Study Flowchart

	Preop (inclusion)	Surgery	Postop day 1
Vitrectomy		X	
Visual acuity	X		X
Eye pressure	X		X
Biomicroscopy	X		X
Ophthalmoscopy	X		X
OCT	X ¹		
Ultrasound	X ²		X ²
Adverse events	X ³		X
Surgical summary		X	

X¹ if required, depending on indication for surgery, e.g.: macular pucker, macular hole, vitreomacular traction, ...

X² if required, depending on indication for surgery, e.g.: vitreous hemorrhage

X³ any pre-operative clinical condition that is known to affect the incidence of (S)AE's during surgery (e.g. zonular dehiscence, tamsulosine medication, axial length, ...)

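### The evening-of-surgery signature conflicts with the promised time to consider, and the plan cannot show whether patients who do not sign that evening differ in complication rate

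*Combined protocol and SAP*

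**What the plan says.** **Time to consider.** Section 9.2 states: "The participant will be allowed as much time as wished to consider the information, and the opportunity to question the Investigator, their GP". Advice from further outside parties is allowed too. The section on patient information and consent in the Good Clinical Practice chapter also promises time for consideration.

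**Time of signature.** Section 9.1: "Patients will be asked for permission for inclusion in the study on the evening of the day of the surgery". It ties this to the surgeon's round of the one-night-stay department: "During that post-operative patient briefing, the surgeon will ask the patient for inclusion in the trial and to sign the informed consent". Section 9.2 closes with the same timing: "For this clinical trial, signature for approval from the patient will be obtained at the evening of the day of the surgery". No later moment is mentioned.

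**Signature as a condition.** Section 9.2: "potential participant must personally sign and date the latest approved version of the informed consent form before the EMR is used for this study". No representative or deferred route is described.

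**Timing elsewhere.** The first column of the flowchart in 7.2 is headed "Preop (inclusion", which puts inclusion before surgery. Section 18.3.2 sets a reporting rule for the interval between consent and first use of the device. That interval does not exist if consent follows surgery.

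**Safeguard.** Section 9.1 recognises that a surgeon might avoid asking high-risk patients. It answers that the investigator will ask every patient operated that day and "keep an (pseudonymized) list of how many patients refused participation". It then treats the bias as removed.

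**The concern.** The primary endpoint is the complication rate (13.1), and the main purpose is intra-operative safety (section 6). By the evening round those events have already happened, so entry to the dataset is decided after the outcome is known.

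A patient who wants to sleep on the decision or telephone the GP is promised that freedom and then has no described way to use it. The same holds for a patient who is not fit to sign a few hours after sedation or general anaesthesia, both of which 11.3 allows. Such patients are not refusals, so the 9.1 list does not record them.

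If they had complications more often than those who signed, the reported rate would be too low. In a safety study that is the unfavourable direction. The missing-data methods in 13.6 cannot help: they relate a missing outcome to measured baseline variables, and a patient who never signed contributes neither. Section 13.8 includes all patients but has no rule for operated patients without a signature.

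**Working it through.** **The plan's own figure.** Section 8.1 expects about 5% complications and recruits 250 to obtain at least 10. Expected events are 250 × 0.05 = 12.5. The exact binomial probability of at least 10 is 0.805. The plan states no probability; 80% is reached at 249 patients, so 250 is reproduced if 80% was intended. There is little slack.

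**Effect of outcome-dependent signing.** Let p be the true rate, c the share of complicated patients who sign and u the share of uncomplicated patients who sign. Then

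observed rate = p·c / [p·c + (1 − p)·u].

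The documents give neither c nor u. The values below are assumptions with u = 0.90. Worked line for p = 0.15, c = 0.80: 0.120 / (0.120 + 0.765) = 0.120 / 0.885 = 13.6%.

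| Signing, complicated v uncomplicated | True 5% | True 15% | True 30% | P(at least 10 events in 250) at true 5% |
|---|---|---|---|---|
| 90% v 90% | 5.0% | 15.0% | 30.0% | 0.81 |
| 88% v 90% | 4.9% | 14.7% | 29.5% | 0.78 |
| 80% v 90% | 4.5% | 13.6% | 27.6% | 0.68 |
| 70% v 90% | 3.9% | 12.1% | 25.0% | 0.52 |

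With equal signing shares there is no bias, however many patients are lost.

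**Scale against sampling error.** At n = 250 the standard error is √(0.15 × 0.85 / 250) = 2.3 points at 15%, and √(0.05 × 0.95 / 250) = 1.4 points at 5%. A 2-point gap in signing moves 15% by 0.3 points, well inside this. A 20-point gap moves it by 2.9 points, more than one standard error.

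**Effect on the test.** Section 13.1 tests the rate against 5%, 15% and 30%, two-sided at 5% (13.3). An exact test against 5% with 250 patients finds an excess at 20 or more events. If the true rate is 10%, the chance of that is 0.88 with equal signing, 0.86 at 88% v 90%, 0.74 at 80% v 90% and 0.52 at 70% v 90%.

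**What a full list would allow.** Suppose (assumed numbers) that 250 are operated, 240 sign and 12 of these have a complication: 12/240 = 5.0%. If none or all of the 10 non-signers had a complication, the rate over all operated patients lies between 12/250 = 4.8% and 22/250 = 8.8%. A count of refusals alone does not supply the 10.

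**The case against.** A reader might infer that patients who had general anaesthesia or a serious complication cannot sign that evening, so that the worst outcomes are lost and the rate is biased downward by design. The documents do not support this:

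- Section 9.1 requires every operated patient to be asked.
- Local anaesthesia alone is permitted (8.2, 11.3). Loss through sedation or general anaesthesia distorts the rate only if type of anaesthesia is linked to complications.
- Most Appendix A events are ocular, such as lens touch, iris trauma or a retinal tear, and need not affect the ability to sign hours later.
- Nothing says that patients are unfit to sign by evening, and late signing is not an exclusion criterion (8.3). Section 9.2 could be read as a general right to time plus a usual moment of signing.
- The informed consent form (Appendix E) was not available for this review and may say more about decision time.

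These points stand, and they reduce the bias from a finding to a possibility. They do not reconcile the two statements in 9.2, correct the flowchart, or provide for the undecided and those unable to sign. The ask-everyone rule addresses the surgeon's choice, not the patient's state or indecision.

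There is also a fair objection to later consent: the patient may then decide after learning the day-1 result, which could itself make participation depend on outcome. This is a reason to keep the window short and to log every status.

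**Conclusion.** The contradiction over consent timing is established from the text: 9.2 against itself and 9.1, with 7.2 and 18.3.2 out of line. It is also established that no route is described for patients undecided or unable to sign that evening, and that the list covers refusals only.

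Downward bias is possible, not demonstrated. It requires signing to be less common after a complication, and the documents are silent on that. Over the assumed gaps of 0 to 20 percentage points, a true 15% would be reported as between 15.0% and 12.1%. The firm conclusion is that the plan, as written, could not tell these cases apart. The point is worth correcting because the correction is cheap.

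**What to change.** 1. In 9.1 and 9.2, state that patients are informed on the evening of surgery and may sign up to and including the existing day-1 visit, and that no EMR data enter the eCRF before signature. The patient stays overnight (11.3) and is seen on day 1 anyway (7.2), so no visit is added. The window should not run to a later standard visit: data acquisition ends after day 1 (5.3, 13.4), and the safety reporting deadlines in 18.3.2 and 18.5.1 would be hard to reconcile with it.
2. Extend the 9.1 list so that every operated patient is counted once, as consented, refused, undecided, unable to sign or not reached. Report these counts beside the complication rate.
3. Correct the flowchart heading in 7.2 so that inclusion follows surgery, and reconcile the consent timing with 18.3.2, including the rule for events between consent and first device use and the 24-hour reporting of serious events.

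**Cost.** A protocol amendment to the ethics committee and eCRF entry up to a day later. Some patients would decide after the day-1 findings are known; the extended list shows how many patients did not join and in which category, but not their outcomes.

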9.3. Withdrawal of participants

Subjects are free to discontinue participation in the investigation at any time, and without prejudice to further treatment. Subjects who discontinue the investigation should always be asked about the reason(s) for their discontinuation and about the presence of any Adverse Event/Adverse Device Effect or Device Deficiency and, if possible, be assessed by an investigator. Adverse Event/Adverse Device Effect should be followed up.

Subjects may be withdrawn from investigation treatment and assessments at any time.

Incorrectly enrolled subjects will be withdrawn from further investigation treatment and assessments. A subject may, however, continue the investigation under special circumstances (i.e. if continuation of investigation treatment or follow-up actions are necessary for the subject's safety and well-being, or if only a follow-up period remains, and the continuation of the investigation is not expected to be associated with any risk or discomfort for the subject)

10. INVESTIGATIONAL DEVICE

10.1. Investigational device details

The device used for this clinical trial and its supplies will have a CE-label. Hence, no FAGG approval will be requested to use the device for this trial.

10.2. Device manufacturer

Manufacturer of devices included in section 10.1 is DORC BV, [name].

10.3. Device accountability

In the hospital, there is a standard procedure for returning faulty products. This procedure will be followed, similar to the standard clinical path.

10.4. Storage conditions

All disposable supplies used with the device come pre-sterilized and will be used before expiration date. The reusable instruments (mainly: phaco handpiece) will be steam-sterilized according to the guidelines provided by the manufacturer.

10.5. Concomitant Treatments

Before, during and after the surgery, the same medication and antiseptic treatment will be applied as in patients following the standard clinical path. This includes:

- Preoperative application of mydriaser to dilate the pupil
- Preoperative antiseptic treatment with betadine
- BSS plus infusion liquid during the surgery
- Intra-operative injection of Mydrane if pupillary dilation is required
- Intra-operative injection of Miostat if pupillary miosis is required
- Injection of parabulbar triamcinolone and clindamycin at the end of the surgery
- Postoperative dexamethasone anti-inflammatory eyedrops

At the discretion of the investigator, additional medication may be prescribed.

10.6. FAGG Approval

Not applicable, see 10.1

11. CLINICAL INVESTIGATION ASSESSMENTS

11.1. Subject Characteristics

During vitrectomy surgery, typical surgical parameters will be recorded:

- Surgical indication
- If combined phaco-surgery is performed: amount of phaco power used
- Staining dyes (if used)
- Amount of laser coagulates (if used)
- Type of tamponade left in the eye: BSS+ liquid, air bubble, air, gas (type + concentration) or silicone oil (type)

11.2. Clinical investigation assessments

Patients that are scheduled for vitrectomy and/or cataract surgery that is commonly performed will be included. The preoperative preparation of the patient and the surgery itself will not be different from the standard of care.

Typical postoperative follow-up after vitrectomy includes the clinical tests to assess that normal postoperative outcome is present, without the presence of adverse events.

Hence, the same clinical data will be collected in the study patients as in patients undergoing the standard-of-care.

11.3. Surgical procedure

The patient will be operated under local anesthesia, local anesthesia with sedation or general anesthesia, depending on the surgeon's and patient's preferences and general status of health. In case of vitrectomy surgery, in case the patient is phakic and over 50 years old, the surgery will be combined with a cataract surgery (phaco-emulsification) in most cases. As in the standard of care, the patients will stay overnight in the hospital after the surgery (one-night stay).

11.4. Safety assessments

The EVA Nexus device and its supplies are CE certified per Medical Device Directive (93/42/EEC) and comply therefore with the safety and performance requirements as stated in the Essential Requirements of this directive. Compliance with applicable safety and performance standards has been confirmed during extensive testing as part of the development process and the associated records are part of the design history file. These records are subject to periodic surveillance audits by Notified Body DEKRA.

11.4.1 Adverse events that do not require reporting

After vitrectomy, the following transient adverse events are commonly present during the first day after surgery, hence will not require reporting:

- Decreased visual acuity compared to preoperative measurement
- Reddish eye
- Moderately and temporarily increased ocular pressure (<35 mmHg)
- Mild to moderate intra-ocular inflammation
- Mild corneal edema In addition see section 18.2.

12. DATA QUALITY ASSURANCE

12.1. Monitoring, Audit and Inspections

Investigator and the institution(s) will permit trial-related monitoring, audits, EC review, and regulatory inspections (where appropriate) by providing direct access to source data and other documents.

12.2. Training of staff

The Principal Investigator will ensure that appropriate training relevant to the investigation is given to the medical, nursing and other staff at the site involved and that new information of relevance to the performance of this investigation is forwarded to the staff involved.

The staff at the investigational site will sign a confirmation document that they are trained.

12.3. Data Management

An eCRF will be created on the RedCap platform. This platform provides all required functionality, security and traceability to be compliant with a CRF. To pseudonymize the patient data in the eCRF, a separate file containing the list of patients linked to the study number will be kept behind the hospital firewall, only accessible by the study personnel involved in this trial.

All documents will be stored safely in confidential conditions. On all clinical investigation-specific documents, other than the signed consent, the participant will be referred to by the clinical investigation participant number/code, not by name.

All clinical investigation documentation will be kept for 25 years from the clinical investigation plan defined end of clinical investigation point. When the minimum retention period has elapsed, clinical investigation documentation will not be destroyed without permission from the sponsor.

13. STATISTICS

13.1. Description of statistical methods

Will be outsourced to a licensed medical statistician (Ars Statistica). An pseudonymizedExcel-export will be generated from the eCRF for statistical analysis.

For the primary endpoint (complication rate of the EVA Nexus), a one-sample proportion test will be performed to test whether the obtained rate is different from rates found in the literature (30%, 15% and 5%).

For the remaining data (demographics and secondary objectives), group comparisons (no complications vs complications) of categorical variables will be analyzed using a Fisher's exact test and group comparisons (no complications vs complications) of continuous variables will be performed using the T-test or the Wilcoxon signed rank test, as appropriate (=when the normality of the residuals and the equality of the variances are met, the T-test will be used, and when the normality of the residuals or the homoskedasticity of the variances will not be met, the Wilcoxon signed rank test will be used). Last, in order to test a first predictive model, a logistic or Poisson regression, as appropriate, with backward selection method will be performed, starting with all variables associated with the target with a p-value lower than 0.1. The final model will contain variables associated with the outcome with a p-value lower than 0.05.

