7. CLINICAL INVESTIGATION DESIGN

7.1 Trial Design

Investigator-initiated, academic, mono-center, prospective, field observation study using a novel CE-labeled surgical platform.

The study will be terminated after a time period of three months. A maximum of 250 patients will be enrolled. The study will consist of 3 patient visits. Study follow-up is 1 day after the date of the vitrectomy surgery.

During surgery, intra-operative complications and issues will be recorded for safety assessment: see list in previous paragraph.

Typical postoperative follow-up after vitrectomy includes the clinical tests to assess that normal postoperative outcome is present, without the presence of adverse events.

Hence, the same clinical data will be collected in the study patients as in patients undergoing the standard-of-care.

This field observation study is conducted to obtain information about the complication rate of the EVA Nexus system which will be compared with the incidence of these complications occurring in surgeries performed using our present DORC EVA platform. ¹⁵⁻¹⁸

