8. CLINICAL INVESTIGATION POPULATION

8.1. Number of participants – sample size analysis

With a complication rate ranging from 5% up to 30% in previous studies, we have no a priori about the complication rate of the EVA Nexus system. We therefore consider a rather conservative hypothesis and expect to have around 5% of complications with the EVA Nexus system. We plan recruit 250 patients in total in order to get at least 10 complications with EVA Nexus. The estimated enrolment time is 6 months.

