13.2. The number of participants

Maximum 250, inclusion time 4 months.

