13.7. Procedures for reporting any deviations from the original statistical plan

The final statistical plan will be agreed prior to final data lock and prior to any analyses taking place. Any deviation thereafter will be reported in the final trial report.

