13.13.3. Inferential statistics

For the primary endpoint (complication rate of the EVA Nexus), a one-sample proportion test will be performed to test whether the obtained rate is different from rates found in the literature (30%, 15% and 5%).

For the remaining data (demographics and secondary objectives), group comparisons (no complications vs complications) of count variables will be analyzed using a Fisher's exact test and group comparisons (no complications vs complications) of continuous variables will be performed using the T-test or the Wilcoxon signed rank test, as appropriate (=when the normality of the residuals and the equality of the variances are met, the T-test will be used, and when the normality of the residuals or the homoskedasticity of the variances will not be met, the Wilcoxon signed rank test will be used). Last, in order to test a first predictive model, a logistic or Poisson regression, as appropriate, with backward selection method will be performed, starting with all variables associated with the target with a p-value lower than 0.1. The final model will contain variables associated with the outcome with a p-value lower than 0.05.

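### The non-parametric fallback for comparing patients with and without complications is named as the signed rank test; the groups are independent, so the name should read Wilcoxon rank-sum (Mann-Whitney).

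*Combined protocol and SAP*

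**What the plan says.** Section 13.1 (Description of statistical methods) covers demographics and secondary objectives. It compares patients without complications to patients with complications, using Fisher's exact test for categorical variables. For continuous variables it says "group comparisons (no complications vs complications) of continuous variables will be performed using the T-test or the Wilcoxon signed rank test, as appropriate". The choice between the two depends on assumption checks: "when the normality of the residuals and the equality of the variances are met, the T-test will be used". Otherwise the fallback applies, in the words that section 13.13.3 (Inferential statistics) also uses: "when the normality of the residuals or the homoskedasticity of the variances will not be met, the Wilcoxon signed rank test will be used".

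Each of the two sections names the signed rank test twice. Neither they nor any other section mentions a rank-sum or Mann-Whitney test. After these comparisons, both sections describe a regression model built by backward selection, "starting with all variables associated with the target with a p-value lower than 0.1". They do not say which test produces that p-value.

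**The concern.** The Wilcoxon signed rank test needs one difference per pair, or a single sample measured against a fixed value. A comparison of patients who had a complication with patients who did not offers neither: each patient is in one group only. Read literally, the plan has no usable fallback for any continuous variable that fails the normality or equal-variance check.

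What is at stake is the set of continuous demographic and secondary comparisons. If the p<0.1 screen takes its p-values from these tests, the list of variables entering the regression is affected too. If the name is not corrected in the final plan, the analyst has to replace the prespecified test after data lock, and section 13.7 would make that a deviation to report.

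**Working it through.** The documents state no figure for this comparison, so there is none to reproduce. The check is whether the named test fits the comparison.

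**1. Are the groups paired?** The design is a single-centre prospective observational study, and the groups are formed by outcome. No matching is described. The naturally paired data are visual acuity and eye pressure, measured before surgery and on day 1 (section 7.2), but the sentence at issue compares groups of patients, not change within a patient. The preparation-time comparison of EVA Nexus with DORC EVA (section 6) concerns separate surgeries and is not described as paired either.

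**2. What was meant?** Two features of the same sentence belong to independent groups: equality of variances is a condition of the two-sample t-test, not of the paired one, and Fisher's exact test is used for the other variable type. The rank test that matches both is the rank-sum test.

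**3. What happens at the expected sizes?** Section 7.1 says "A maximum of 250 patients will be enrolled". Section 8.1 expects about 5% complications and cites previous rates of 5% to 30%; section 13.1 tests against 5%, 15% and 30%. Group with complications = N × rate:

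- 250 × 0.05 = 12.5, about 12 vs 238
- 250 × 0.15 = 37.5, about 38 vs 212
- 250 × 0.30 = 75, so 75 vs 175

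A standard signed rank routine (SciPy) stopped with an error at all three splits. The rank-sum test runs. Under normal data with equal spread its simulated two-sided error at nominal 5% was 4.8%, 4.9% and 4.9% (20,000 replicates each).

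**4. Could it run by accident?** Only with equal groups. At N = 250 and a 30% rate, P(125 vs 125) = C(250,125) × 0.3^125 × 0.7^125 ≈ 1.7 × 10⁻¹¹, and it is smaller still at 15% and 5%. Even then the pairing would be arbitrary.

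**5. Side check on the branching rule (optional remark only).** The rule also uses the rank test when equal variance alone fails. The documents give no standard deviations, so the ratio of smaller- to larger-group SD is assumed. For normal data with equal means at 12 vs 238, nominal 5%:

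| SD ratio (assumed) | Rank-sum rejects |
|---|---|
| 0.5 | 0.4% |
| 1 | 4.8% |
| 2 | 13.1% |
| 3 | 17.2% |

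Welch's t-test stays between 4.8% and 5.2% in these cells. Running the whole rule with only the name corrected gives 14.2% at ratio 2 (8,000 replicates; Shapiro-Wilk and Levene checks at 5% are assumed, because the plan names none).

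**The case against.** The case for leaving this alone is that the slip is self-evident. Its own sentence shows the intended test, a professional statistician will do the analysis, and the plan is not yet final: "The final statistical plan will be agreed prior to final data lock and prior to any analyses taking place". The comparisons are secondary, and no decision hangs on them. All of this stands, and it sets the weight. It does not remove the point, because both statistical sections carry the same wrong name and nothing corrects it.

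A reader might infer three stronger things that the documents do not support.

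- **That wrong p-values would be reported unnoticed.** At the unequal group sizes the plan implies, the call fails. The failure reflects how one routine behaves, but the reason behind it, that no pairs exist, is general.
- **That the choice of substitute would be open to the data.** There is one obvious substitute, so little room exists for that.
- **That the rule must move to Welch's t-test.** The inflation in step 5 rests on assumed SD ratios and on reading the rank-sum test as a test of equal means, a null hypothesis the plan does not state. As a test of equal distributions, rejecting when spreads differ is not a false positive. Welch also has a price: if variances are in fact equal, at an effect giving the ordinary t-test about 80% power, simulated power at 12 vs 238 falls from 79.6% to 73.5%. It also helps little outside normal data. A rule using Welch when normality holds and rank-sum otherwise was simulated at 12 vs 238 with t(5) data at SD ratios 2 and 3. It rejected 11.0% and 14.0% of the time, against 12.4% and 15.3% with the name alone corrected. With lognormal data the two rules rejected equally often.

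**Conclusion.** The point holds, as a minor one. The signed rank test is the wrong test for independent groups of patients, and both sections need the correction. This rests only on the absence of pairing and does not depend on the complication rate or on how many patients are enrolled. That the rank-sum test was intended is an inference, but a strong one.

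The slip does not reach the primary one-sample proportion test or the sample size. It is confined to continuous demographic and secondary comparisons, plus the regression screen if these tests feed it.

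The behaviour of the rank-sum test under unequal spread is a separate and optional remark. Its size depends on SD ratios that the documents do not give, and the alternative is a trade-off, so it is not a defect that has to be repaired.

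**What to change.** In sections 13.1 and 13.13.3, replace Wilcoxon signed rank test with Wilcoxon rank-sum (Mann-Whitney) test at every mention: two in each section, four in all. Make the change when the final statistical plan is agreed, before data lock and before any analysis (section 13.7). It is a wording change with no effect on data collection, sample size or the primary analysis.

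Optional, and not part of the fix: when the final plan is written, the statistician may consider Welch's t-test for variables that are normal but unequal in spread, weighing the roughly six points of power it costs at 12 vs 238 if variances are equal (79.6 − 73.5 = 6.1).
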